# **Oral Drug Administration (Treatment C):**

Study drug will be given orally and be administered with approximately 240 mL of water. Subjects will be instructed not to crush, split, or chew the study drug tablets

The pharmacy manual will provide further application information.

# 9.3.2. Procedures on Dosing Days (Days 1, 8, 15, 22, & 29) during Period 1

The following assessments will be performed on dosing days during Period 1 of Treatment Phase:

1. Subjects will be instructed to shower from 1 to 2 hours prior to each TDS application. If showers are not taken, the following will be performed within 1 to 2 hours prior to each TDS application, the application area will be washed with room temperature water using a wet washcloth. The application site will be patted dry and will be checked for irritancy.

- 2. Subjects will receive a light meal approximately 30 minutes prior to TDS application or oral Aricept administration.
- 3. Vital signs after a minimum of 3 minutes of rest (respiratory rate, pulse rate, blood pressure, oral temperature) will be collected at times listed in **Section 13.4**.
- 4. Blood samples for pharmacokinetics will be collected at times listed in Section 14.1.
- 5. The site receiving the TDS should be assessed for skin irritation prior to TDS application (if the score is greater than zero another site must be selected).
- 6. The TDS is applied to the subject within 120 minutes of opening/removing from the packaging and the application area will be identified with a template overlay. The TDS will be placed at the designated application site and firm pressure will be applied immediately over the TDS for approximately 20 seconds using the palm of the hand on each TDS to ensure adhesion. The area selected should not be oily, damaged, or irritated and should not be exposed to sunlight. The exact clock time of TDS application will be recorded for the start of TDS application. No taping of the Transdermal Delivery Systems will be allowed.
- 7. A photograph of the TDS will be taken immediately after application and at all adhesion timepoints.
- 8. Patch Adhesion Assessments will be performed at times listed in Section 15.1.
- 9. Review of concomitant medications, treatment and/or therapies.
- Assessment of adverse events. While subjects are in the research clinic, AEs will be monitored continuously and solicited using a non-leading question at times listed in Section 13.8. The inquiry using non-leading questions will be performed after all other procedures are conducted for the specified time points.

The PK samples will be collected at the nominal time points  $\pm 5$  minutes.

# 9.3.3. Procedures for In-Clinic Days during Period 1

The following assessments will be performed during the in-clinic days of period 1:

- 1. Blood samples for pharmacokinetics will be collected at times listed in Section 14.1.
- 2. TDS Adhesion Assessments will be performed at times listed in Section 15.0.
- 3. A photograph of the TDS will be taken at adhesion timepoints.
- 4. Review of concomitant medications, treatment and/or therapies

Assessment of adverse events. While subjects are in the research clinic, AEs will be monitored continuously and solicited using a non-leading question at times listed in Section 13.8. The inquiry using non-leading questions will be performed after all other procedures are conducted for the specified time points.

#### 9.4. Procedures on TDS Removal Days (Days 8, 15, 22, 29 & 36) during Period 1

- 1. Vital signs after a minimum of 3 minutes of rest (respiratory rate, pulse rate, blood pressure, oral temperature) will be collected at times listed in **Section 13.4.**
- 2. Immediately after removal, used TDSs will be collected and returned to the Sponsor. As soon as the TDS has been removed from the skin, the used TDS will be placed, adhesive side down, on to a new release liner or folded in half and placed into a foil pouch. The sealed, labeled foil pouch and the corresponding original labeled patch pouch will then be inserted into a plastic bag and stored at approximately -20°C (-4°F) The used TDS will be shipped to the Sponsor, for residual drug determination. Additional instructions regarding application and removal of the TDS are provided in the Pharmacy Manual.
- 3. TDS site Irritation Assessments will be obtained at times listed in Section 16.1.
- 4. Blood samples for pharmacokinetics will be collected at times listed in Section 14.1.
- 5. Obtain blood sample for chemistry, hematology, coagulation, and urinalysis tests. (Day 36).
- 6. Urine pregnancy tests for females only (Day 36).
- 7. Perform the Columbia Suicide Severity Rating Scale (C-SSRS) "Since Last Visit" version. Subjects with clinically significant suicidal ideation based on the C-SSRS assessment, in the opinion of the Investigator, will be excluded from further participation in the study, and further evaluation and/or preventive intervention steps for suicidal behavior will be taken, at the discretion of the Investigator (Day 36).
- Patch Adhesion Assessments and photographs will be performed at times listed in Section 15.0
- 9. Review of concomitant medications, treatment and/or therapies
- Assessment of adverse events. While subjects are in the research clinic, AEs will be monitored continuously and solicited using a non-leading question at times listed in Section 13.8. The inquiry using non-leading questions will be performed after all other procedures are conducted for the specified time points.

#### 9.4.1. Study Drug Administration (Period 2 & 3) Treatment B

The following assessments will be performed on dosing days during Period 2 & 3 of Treatment B Phase (Study Days 37, 44, 51, 58, 65, 73, 80, 87, 94, & 101):

- 1. Subjects will be instructed to shower from 1 to 2 hours prior to each TDS application. If showers are not taken, the following will be performed within 1 to 2 hours prior to each TDS application, the application area will be washed with room temperature water using a wet washcloth. The application site will be patted dry and will be checked for irritancy.
- 2. Subjects will receive a light meal approximately 30 minutes prior to TDS application
- 3. Vital signs after a minimum of 3 minutes of rest (respiratory rate, pulse rate, blood pressure, oral temperature) will be collected at times listed in **Section 13.4**.
- 4. Blood samples for pharmacokinetics will be collected at times listed in Section 14.1.
- 5. The site receiving the TDS should be assessed for skin irritation prior to TDS application (if the score is greater than zero another site must be selected).
- 6. The TDS is applied to the subject within 120 minutes of opening/removing from the packaging and the application area will be identified with a template overlay. The TDS will be placed at the designated application site and firm pressure will be applied immediately over the TDS for approximately 20 seconds using the palm of the hand on each TDS to ensure adhesion. The area selected should not be oily, damaged, or irritated and should not be exposed to sunlight. The exact clock time of TDS application will be recorded for the start of TDS application. No taping of the Transdermal Delivery Systems will be allowed.
- 7. A photograph of the TDS will be taken immediately after application and at adhesion timepoints listed in **Section 15.0**.
- 8. Patch Adhesion Assessments will be performed at times listed in Section 15.0
- 9. Review of concomitant medications, treatment and/or therapies.
- Assessment of adverse events. While subjects are in the research clinic, AEs will be monitored continuously and solicited using a non-leading question at times listed in Section 13.8. The inquiry using non-leading questions will be performed after all other procedures are conducted for the specified time points.

The PK samples will be collected at the nominal time points  $\pm 5$  minutes.

#### 9.4.2. Procedures on In-Clinic Days Period 2 & 3 Treatment B & C

The following assessments will be performed during the in-clinic days of Periods 2 &3:

- 1. Blood samples for pharmacokinetics will be collected at times listed in Section 14.1.
- TDS Adhesion Assessments will be performed at times listed in Section 15.0 Treatment B only. A photograph of the TDS will be taken at adhesion timepoints listed in Section 15.0 Treatment B only
- 3. Review of concomitant medications, treatment and/or therapies
- Assessment of adverse events. While subjects are in the research clinic, AEs will be monitored continuously and solicited using a non-leading question at times listed in Section 13.8. The inquiry using non-leading questions will be performed after all other procedures are conducted for the specified time points.

# 9.4.3. Procedures on TDS Removal Day Treatment B Periods 2 & 3 (Days 44, 51, 58, 65, 72, 80, 87, 94, 101, 108):

- 1. Vital signs after a minimum of 3 minutes of rest (respiratory rate, pulse rate, blood pressure, oral temperature) will be collected at times listed in **Section 13.4.**
- 2. Immediately after removal, used TDSs will be collected and returned to the Sponsor. As soon as the TDS has been removed from the skin, the used TDS will be placed, adhesive side down, on to a new release liner or folded in half and placed into a foil pouch. The sealed, labeled foil pouch and the corresponding original labeled patch pouch will then be inserted into a plastic bag and stored at approximately -20°C (-4°F). The used TDS will be shipped to the Sponsor, for potential residual drug determination. Additional instructions regarding application and removal of the TDS are provided in the Pharmacy Manual.
- 3. TDS site Irritation Assessments will be obtained at times listed in Section 16.0
- 4. Blood samples for pharmacokinetics will be collected at times listed in Section 14.1.
- 5. Obtain blood sample for chemistry, hematology, coagulation, and urinalysis tests. (Day 72).
- 6. Urine pregnancy tests for females only (Day 72).
- 7. Perform the Columbia Suicide Severity Rating Scale (C-SSRS) "Since Last Visit" version. Subjects with clinically significant suicidal ideation based on the C-SSRS assessment, in the opinion of the Investigator, will be excluded from further participation in the study, and further evaluation and/or preventive intervention steps for suicidal behavior will be taken, at the discretion of the Investigator (Day 72).

- 8. Patch Adhesion Assessments and photographs will be performed at times listed in Section 15.0.
- 9. Review of concomitant medications, treatment and/or therapies
- Assessment of adverse events. While subjects are in the research clinic, AEs will be monitored continuously and solicited using a non-leading question at times listed in Section 13.8. The inquiry using non-leading questions will be performed after all other procedures are conducted for the specified time points

# 9.4.4. Procedures for Drug Administration Treatment C (Period 2 & 3)

The following assessments will be performed for drug administration for during Period 2 & 3):

- 1. Subjects will receive a light meal approximately 30 minutes prior to drug administration.
- 2. Vital signs after a minimum of 3 minutes of rest (respiratory rate, pulse rate, blood pressure, oral temperature) will be collected at times listed in **Section 13.4**.
- 3. Blood samples for pharmacokinetics will be collected at times listed in Section 14.1.
- 4. Randomized subjects will receive 10 mg Aricept® donepezil (1 x 10 mg/day tablet) administered QD for 35 consecutive days during either Period 2 or Period 3. Study drug will be given orally and be administered with approximately 240 mL of water. Subjects will be instructed not to crush, split, or chew the study drug tablets.
- 5. Water will be allowed ad libitum up to 1 hour prior to dose administration. No water maybe consumed for 1-hour prior through 1 hour after dosing (except for water needed to administer study drug). After 1 hour following dose administration, subjects may drink water ad libitum.
- 6. Review of concomitant medications, treatment and/or therapies.
- Assessment of adverse events. While subjects are in the research clinic, AEs will be monitored continuously and solicited using a non-leading question at times listed in Section 13.8. The inquiry using non-leading questions will be performed after all other procedures are conducted for the specified time points.

#### 9.4.5. End of Treatment (Day 109)

The end of the treatment phases of the study is Day 109. After all procedures during the Treatment Phase are conducted including the collection of the 168-hour blood sample after the last dose of study drug, the following End-of-Treatment procedures will be conducted:

- 1. Complete physical examination.
- 2. Body weight.
- 3. Clinical laboratory tests (chemistry, hematology, coagulation, and urinalysis). Samples for clinical laboratory tests at the end of treatment can be collected under non-fasted conditions.
- 4. Urine pregnancy test (females only).
- 5. Vital signs after a minimum of 3 minutes of rest (respiratory rate, pulse rate, blood pressure, oral temperature).
- 6. 12-lead ECG will be obtained after the subject has been in the supine position for at least 3 minutes.
- 7. Assessment of the Columbia Suicide Severity Rating Scale (C-SSRS), "Since Last Visit" version. If a subject has a clinically significant suicidal ideation based on the C-SSRS assessment, in the opinion of the Investigator, further evaluation and/or preventive intervention steps for suicidal behavior will be taken, at the discretion of the Investigator.
- 8. Review of concomitant medications, treatment and/or therapies.
- 9. Assessment of adverse events.

Subjects will be discharged from the research clinic when the Investigator determines that the subjects are medically stable, and all end-of-treatment procedures are completed.

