#### 9.1. Screening Procedures

Subjects will complete the screening visit within 28 days (Day -28 to Day -1) of admission to the in-clinic visit of the Treatment Phase (Day -1). Prior to conducting any study-related activities including screening procedures, written Informed Consent and the Health Insurance Portability and Accountability Act (HIPAA) authorization must be signed and dated by the subject.

The following information collection/assessments will be performed at the Screening Visit:

- 1. Informed Consent and HIPAA authorization by the subject.
- 2. Subject demographics including date of birth, sex, race, and ethnicity.
- 3. Review of inclusion/exclusion criteria to determine study eligibility.
- 4. Record medical history including skin type assessment, chronic conditions, relevant surgical procedures (with start date) history of alcohol and recreational drug use, smoking status, evaluation of drug and alcohol use and personal habits affecting the skin (example: tanning, hair removal, and application of tattoos).
- 5. Fitzpatrick skin type score: Type I always burns, never tans, Type II usually burns, tans with difficulty, or Type III may burn initially, but tans easily.
- 6. A complete physical examination with back evaluation and personal habits affecting the skin (example: tanning, hair removal, and application of tattoos).
- 7. Body weight, height, and BMI.
- 8. Vital signs after a minimum of 3 minutes of rest (respiratory rate, pulse rate, blood pressure, and oral temperature).
- 9. 12-lead electrocardiogram (ECG) after subject has been in supine position for a minimum of 3 minutes. Abnormal ECGs may be repeated for confirmation in which case only the repeated ECG will be recorded. The QT interval corrected for heart rate will be calculated with Fridericia's formula (QTcF).

- 10. Clinical laboratory tests (chemistry, hematology, coagulation, and urinalysis) obtained under fasted conditions. During the Screening Period, Clinical Laboratory Measurements may be repeated at the discretion of the Investigator.
- 11. Blood samples for Serology (HIV antibody, hepatitis B surface antigen and hepatitis C virus antibody).
- 12. Urine samples will be tested for alcohol, drugs of abuse (amphetamines, methamphetamines, benzodiazepines, barbiturates, cannabinoids, cocaine, and opioids) If the test is positive for any of the tested analytes, the subject will be excluded from study participation.

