# 9.2. Check-In Procedures (Day -1)

Subjects who meet the inclusion/exclusion criteria during Screening, will be checked into the research clinic on Day -1, the day before treatment with study drug. Subjects will undergo the following procedures upon check-in:

- 1. Review of inclusion/exclusion criteria to determine whether subjects continue to meet study eligibility.
- 2. Update medical history.
- 3. Back application site evaluation and clip application site hair as needed.
- 4. Vital signs after a minimum of 3 minutes of rest (respiratory rate, pulse rate, blood pressure, and oral temperature). Vital signs will be taken at least 12 hours prior to the

subject receiving their first dose of study drug on Day 1.

- 5. 12-lead electrocardiogram (ECG) after subject has been in supine position for a minimum of 3 minutes. Abnormal ECGs may be repeated for confirmation in which case only the repeated ECG will be recorded. The QT interval corrected for heart rate will be calculated with Fridericia's formula (QTcF).
- 6. Perform the Columbia Suicide Severity Rating Scale (C-SSRS) "Since Last Visit" version. Subjects with clinically significant suicidal ideation based on the C-SSRS assessment, in the opinion of the Investigator, will be excluded from further participation in the study, and further evaluation and/or preventive intervention steps for suicidal behavior will be taken, at the discretion of the Investigator.
- 7. Clinical laboratory tests (chemistry, hematology, coagulation, and urinalysis) will be obtained.
- 8. Urine samples will be tested for alcohol, cotinine, drugs of abuse: (amphetamines, methamphetamines, benzodiazepines, barbiturates, cannabinoids, cocaine, and opioids) If the test is positive for any of the tested analytes, the subject will be excluded from study participation.
- 9. Coronavirus (COVID-19) test. A diagnostic test to determine if an active coronavirus infection is present. If the test is for the virus is detected, the subject will be excluded from study participation
- 10. A urine pregnancy test will be performed. A positive pregnancy test will exclude a subject from enrollment into the study.
- 11. Review of concomitant medications, treatment and/or therapies.

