#### 9.5.2. Early Termination (ET)

Early Termination (ET) from the study is defined as withdrawal during the Treatment Phase after at least one dose of study drug is administered. The ET Visit is not required for subjects who screen fail before the administration of the first dose of study drug.

If possible, subjects who terminate early will complete all study procedures post-dose study drug (including PK sample collections) before starting ET procedures. The following procedures will

be performed at ET visits:

- 1. Complete physical examination.
- 2. Vital signs (respiratory rate, pulse rate, blood pressure, and oral temperature) after subject has been sitting for a minimum of 3 minutes.
- 3. 12-lead ECG after subject has been in supine position for a minimum of 3 minutes.
- 4. Clinical laboratory tests (chemistry, hematology coagulation, and urinalysis). Samples for clinical laboratory tests at Early Termination can be collected under non-fasted conditions.
- 5. Urine pregnancy tests (for females only)
- 6. Assessment of the Columbia Suicide Severity Rating Scale (C-SSRS), "Since Last Visit" version. If a subject has a clinically significant suicidal ideation based on the C-SSRS assessment, in the opinion of the Investigator, further evaluation and/or preventive intervention steps for suicidal behavior will be taken, at the discretion of the Investigator.
- 7. If applicable, perform skin irritation/tolerability assessments, adhesion assessments and adhesion photographs.
- 8. Review of concomitant medications, treatment and/or therapies.
- 9. Assessment of adverse events.

Subjects will be discharged from the study clinic when the Investigator determines that the subjects are medically stable and, if possible, after all ET procedures are completed.

At the discretion of the Investigator, ensuring the safety of the subjects, any ET procedures that were already performed on the same day as part of the procedures of the current treatment phase, do not need to be repeated.

Subjects who withdraw early from the study and complete the above ET procedures will not return for a Follow-Up Visit. Therefore, the ET Visit is the EOS for these subjects.

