## **12.6.** Clinical Laboratory Measurements

All clinical laboratory samples will be sent to a local laboratory for analysis. Up to approximately 40 mL of blood will be collected for clinical chemistries, hematology, and pregnancy test (if applicable) from each subject during the study. During the Screening Period, Clinical Laboratory Measurements may be repeated at the discretion of the Investigator.

The Clinical Laboratory evaluations will consist of the following:

- Total Hematology as well as differential and Coagulation: red blood cell count, white blood cell count with differential (neutrophils, lymphocytes, monocytes, eosinophils, basophils), hemoglobin, hematocrit and platelets, Prothrombin Time (PT) and Partial Thromboplastin Time (PTT).
- Serum Chemistry: aspartate aminotransferase (AST), alanine aminotransferase (ALT), albumin, alkaline phosphatase, bicarbonate, total bilirubin, blood urea nitrogen, phosphorus (inorganic) calcium, chloride, creatine phosphokinase, creatinine, gamma glutamyl transferase, glucose, lactate dehydrogenase, potassium, sodium, total protein, and uric acid.
- Urinalysis: microanalysis for specific gravity, pH, protein, glucose, ketones, blood, nitrites, leukocytes. If positive for blood, protein or nitrites, a microscopic examination will be performed.
- Serology: hepatitis B surface antigen, hepatitis C antibody and human immunodeficiency virus antibody.
- Pregnancy Tests: will be performed for all female subjects. A serum β-hCG pregnancy test will be performed at Screening. A urine pregnancy test will be performed at check-in, Day 36, Day 72, Day 109, and the Early Termination visit,. A positive pregnancy test will exclude a subject from enrollment into the study. A positive urine pregnancy test will be confirmed with a serum β-hCG pregnancy test.
- Urine Screen for Alcohol, Drugs of Abuse: Urine samples will be tested for alcohol, drugs of abuse (amphetamines, methamphetamines, benzodiazepines, barbiturates, cannabinoids, cocaine, and opioids) at Screening and at check-in of the Treatment Phase. If the test is positive for any of the tested analytes the subject will be excluded from further study participation.

• Laboratory safety tests will be obtained at the Screening visit, Day -1, Day 36, Day 72, Day 109, and at the Early Termination visit. In addition, laboratory safety tests may be performed at various unscheduled time points if deemed necessary by the investigator.

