6.11.2 Laboratory Data

Samples for clinical laboratory tests will be collected at screening, prior to start of Period 1 treatment (Treatment A), at the end of treatment within each study period, and in the event of premature study termination. Descriptive statistics for the the observed values and change from baseline (continuous data) will be presented by treatment for hematology, serum chemistry, coagulation, and urinalysis parameters at the following time points:

- Screening,
- Baseline (last available measurement prior to start of Period 1 treatment),
- End of treatment (Day 36 after TDS application/first dose within study period),
- Early termination (last available sample collected for subjects who prematurely terminated from the study).

Each measurement (continuous data) will be classed as below (low), within (normal), or above (high) normal range, based on ranges supplied by the laboratory used. Shift tables in relation to the normal range from Screening visit to the End of Treatment (EoT) or ET visit will be presented.

A listing of any abnormal laboratory measurements recorded throughout the study will be presented.

All laboratory data, including serology, urine drug screening tests, COVID-19 testing data and pregnancy test data will be listed.

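### Safety labs are fasted at Screening but may be non-fasted at Day 109 and Early Termination, so the planned glucose shift tables may show meal effects with no drug effect

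*Protocol*

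**What the plan says.** Protocol 12.6 fixes the visits: "Laboratory safety tests will be obtained at the Screening visit, Day -1, Day 36, Day 72, Day 109, and at the Early Termination visit". It sets no fasting rule, and it includes glucose in the serum chemistry panel. Fasting state is addressed only in the visit sections:

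- Screening (9.1, item 10): "Clinical laboratory tests (chemistry, hematology, coagulation, and urinalysis) obtained under fasted conditions".
- Day -1 (9.2, item 7): "Clinical laboratory tests (chemistry, hematology, coagulation, and urinalysis) will be obtained", with no condition.
- Day 36 (9.4, item 5) and Day 72 (9.4.3, item 5): samples are required, with no condition.
- Day 109 (9.4.5, item 3): "Samples for clinical laboratory tests at the end of treatment can be collected under non-fasted conditions".
- ET (9.5.2, item 4): "Samples for clinical laboratory tests at Early Termination can be collected under non-fasted conditions".

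SAP 6.11.2 classes each continuous value as low, normal or high on the laboratory's own range and then states: "Shift tables in relation to the normal range from Screening visit to the End of Treatment (EoT) or ET visit will be presented". The serum chemistry version is Table 14.3.7.4. The change-from-baseline summaries start elsewhere, at the last value before Period 1 treatment, which is normally Day -1. Neither document records fasting state, applies a separate non-fasted range, excludes glucose or adds a caveat.

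**The concern.** The shift table starts at the only visit where fasting is required. It ends at visits that include the only two where fasting is expressly waived. A reader of the table will take a move from normal to high as something that happened on treatment. For an analyte that rises after eating, it may only mean that the second sample followed a meal.

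Safety and tolerability form a stated objective, and laboratory evaluations are a named safety endpoint (SAP 3.3). What is at stake is the reading of the glucose rows in those tables. No hypothesis test or decision rule depends on them.

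**Working it through.** There is no planned figure to reproduce, so the check is mainly a comparison of the text.

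**1. Fasting state by visit**

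| Visit | Fasting state | Role in SAP 6.11.2 |
|---|---|---|
| Screening | required | start of shift tables |
| Day -1 | not stated | usual baseline for change tables |
| Day 36 (end of Period 1, all on 5 mg TDS) | not stated | end of treatment, 5 mg TDS |
| Day 72 (end of Period 2) | not stated | end of treatment, 10 mg TDS or Aricept |
| Day 109 | non-fasted allowed | end of treatment, Period 3 |
| ET | non-fasted allowed | end of shift for early withdrawals |

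The explicit mismatch is Screening against Day 109 and Screening against ET. For Days 36 and 72, comparability with Screening is undefined. For the change tables it is also undefined, because Day -1 has no stated condition.

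**2. Which day ends Period 3**

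SAP 6.11.2 places end of treatment at Day 36 of each period. Period 3 starts on Study Day 73, so this is 73 + 36 - 1 = Study Day 108. Protocol 9.4.5, 12.6 and footnote 3 to the Schedule of Events put the sample on Day 109, where the allowance applies. In the schedule grid, as extracted, the laboratory mark appears under Days 72 and 108, but the extraction may have displaced it. The two documents need reconciling on this day.

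**3. Who is exposed**

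All subjects take 5 mg TDS in Period 1. The order of 10 mg TDS and Aricept is randomised over Periods 2 and 3. With 48 planned completers split about equally between sequences, about 48 / 2 = 24 per 10 mg treatment finish in Period 3 and have the Day 109 sample.

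**4. Illustration of size (all glucose inputs assumed, none from the documents)**

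The upper limit is 99 mg/dL, the fasted mean m is 85 or 90, and there is no drug effect. Screening value: F = m + b + e1. Later value: E = m + d + b + e2, where d is the mean meal effect. The between-subject SD of b is 6. The SD of e1 is 5, and the SD of e2 is 5 if d = 0 and 10 otherwise. The quantity of interest is the normal-to-high shift, P(F ≤ 99 and E > 99), estimated from 400,000 simulated subjects per row.

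| d (mg/dL) | m = 85 | m = 90 | expected of 24 |
|---|---|---|---|
| 0 | 2.6% | 7.3% | 0.6 to 1.7 |
| 5 | 20.1% | 28.8% | 4.8 to 6.9 |
| 10 | 33.9% | 43.8% | 8.1 to 10.5 |
| 20 | 66.2% | 70.7% | 15.9 to 17.0 |
| 30 | 87.9% | 83.9% | 20.1 to 21.1 |

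Part of the step from d = 0 to d = 5 comes from the wider spread assumed for fed samples. The rows with d > 0 also treat every later sample as fed, which the protocol allows but does not require. The share of values above the limit at a single visit would be a different and larger quantity, because it counts subjects who were already high at Screening.

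**The case against.** The strongest reply is that the wording is permissive. Day 109 and ET samples can be non-fasted, but many may be taken before breakfast. The tables are descriptive, the panel has no lipids, abnormal values and all laboratory data are listed, and unscheduled repeats are allowed. An isolated glucose flag could therefore be reviewed case by case. All of this stands, and it limits the point to what the tables may show. It does not remove the point, because no fasting state is recorded and a reviewer could not tell a fed flag from a fasted one.

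A second reply is that the SAP's end of treatment is Study Day 108, which the Day 109 allowance does not literally cover. That conflict is real, but three places in the protocol put the sample on Day 109, and the ET allowance is unaffected.

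Two stronger readings are tempting. A reader might infer a false dose effect: 5 mg always ends on Day 36, while about half of each 10 mg treatment ends on Day 109. That requires Days 36 and 72 to be drawn fasted and Day 109 fed, and the documents state neither. The 5 mg comparison is also confounded with period already, since everyone takes 5 mg first. A reader might also infer that the change-from-baseline tables mix conditions. With Days -1, 36 and 72 unspecified, they may or may not.

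**Conclusion.** The point holds in a limited form. The Screening-to-end-of-treatment and Screening-to-ET shift tables compare a required fasted sample with one that may be non-fasted, and nothing in the SAP handles the difference. They may therefore show normal-to-high glucose shifts with no drug effect.

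The consequence is confined to descriptive safety tables and mainly to glucose. Randomised order spreads any Day 109 effect about equally over 10 mg TDS and Aricept, and bioequivalence is unaffected. The documents do not allow the size to be derived. The simulated rates depend on assumed glucose values and on how many samples are in fact fed; they support the direction only. The documents do not support saying that the tables will report meal effects, or that these will look like a dose effect. The correction is worth making because it is cheap.

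**What to change.** **Protocol.** Put one visit-wide rule in 12.6, for all treatments: scheduled safety labs at Day -1, Day 36, Day 72 and the end of Period 3 are drawn fasted, as at Screening. Delete the non-fasted allowance in 9.4.5, item 3. The rule belongs in 12.6 because 9.4.3 covers Treatment B only and 9.4.4 (Aricept) has no laboratory item. A rule placed in 9.4.3 would leave Day 72 fasted for one 10 mg treatment and unspecified for the other. Day -1 must be included because it is normally the baseline for the change tables; leaving it optional could create a new mismatch there.

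**Early Termination.** Keep the allowance, record fasting status, and list non-fasted glucose separately instead of entering it in the shift and change tables. State this in SAP 6.11.2.

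**Reconcile** the SAP's Day 36 of Period 3 (Study Day 108) with the protocol's Day 109.

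**If samples are already collected,** as the post-database-lock addendum implies, restrict the glucose rows to samples known to be fasted where source records allow. Otherwise add a footnote; that addendum already adds explanatory footnotes to other tables.

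**Cost.** A later breakfast on those mornings, a fasted check-in draw and one extra recorded item. Subjects are confined until Day 109, no dose is scheduled on Days 36, 72, 108 or 109, and protocol 10.2 already lets mealtimes move around study procedures.
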